- **Process for Aim 1b:** MAGE is a metric of glycemic variability that can be measured from CGM, but not from infrequent (daily) monitoring. Thus, among CGM patients only, we will measure the six-month longitudinal change in 24-hr average MAGE. Upon computing each CGM patient's daily MAGE, we will use patient-level hierarchical modeling (generalized linear mixed models) to estimate the overall sixmonth longitudinal trend in MAGE.

Specific Aim 1c: Measure longitudinal change in daily coefficient of variation (C_v) of blood glucose in CGM

- **Hypothesis for Aim 1c:** The patient-level daily C_v of blood glucose will decrease over six months of CGM.
- **Process for Aim 1c:** Like that of MAGE, C_v of blood glucose is a metric of glycemic variability that requires near continuous monitoring. Thus, among CGM patients only, we will measure the six-month longitudinal change in daily C_v of blood glucose using the standard equation: $C_v = \sigma/\mu$. Once we have computed each CGM patient's daily C_v of blood glucose, we will use patient-level hierarchical modeling (generalized linear mixed models) to estimate the overall six-month longitudinal trend in C_v of blood glucose. Additionally, we will report the patient- and group-level distributions in daily blood glucose extrema (i.e., minimum and maximum).

Specific Aim 1d: Measure longitudinal change in overall blood glucose range and “time in range” ($\max \text{Range} - \min \text{Range}$) in CGM

- **Hypothesis for Aim 1d:** The patient-level daily blood glucose range will decrease and time in range (which is defined by glucose levels from 70 to 180) will increase over six months of CGM usage.
- **Process for Aim 1d:** Again, like MAGE and C_v , the blood glucose range is a metric of glycemic variability that is most meaningful with near continuous monitoring. So, among CGM patients only, we will measure the blood glucose range for the i th day as $\text{Range}_i = \max \text{HbA1c}_i - \min \text{HbA1c}_i$, and then use patient-level hierarchical modeling (e.g., generalized linear mixed models) to estimate the overall six-month longitudinal trend in HbA1c range.

Specific Aim 1e: Measure the effect of CGM vs. the standard finger-prick protocol on frequency of hypoglycemic events

- **Hypothesis for Aim 1e:** The patient-level six-month reduction in frequency of hypoglycemic events will be greater among those randomized to CGM than that among those randomized to control.

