- **Process for Aim 1e:** Measure the patient-level change in rate of hypoglycemic events as the patient-level slope of the six-month linear change in the so-called “intensity” (λ) of the estimated nonhomogeneous Poisson point process. Once we’ve computed each patient’s six-month linear change in λ , we will compare the distributions between randomized groups. Note that the motivation for measuring change in frequency as the slope of λ estimated from a non-homogeneous Poisson process is that it allows us to compare changes in frequency of hypoglycemic events between groups with different modes of monitoring (continuous vs daily).

Aim 2: Assess impact of CGM on healthcare utilization and cost

Specific Aim 2a: Measure the effect of CGM vs. standard finger-prick protocol on healthcare utilization

- **Hypothesis for Aim 2a:** The count of primary care, specialist, and emergency department visits or hospital stays over six months will be fewer among those randomized to CGM than that among those randomized to standard finger-prick protocol.
- **Process for Aim 2a:** For each patient, count their visits to a primary care provider or specialist or emergency department/hospital admission. Next, compare the distributions of visit counts between randomized groups using a Poisson test, aggregated as well as stratified by visit type. Other metrics for evaluating utilization may include: current HEDIS performance on diabetes and behavioral health measures, coding specificity for diabetes, emergency department visit per 1000 rate, overall and for patients with diabetes, and hospitalization per 1000 rate related to diabetes.

Specific Aim 2b: Measure the effect of CGM vs standard finger-prick protocol on cost

- **Hypothesis for Aim 2b:** The total variable cost associated with healthcare services/visits over six months will be fewer among those randomized to CGM than that among those randomized to standard fingerprick protocol.
- **Process for Aim 2b:** For each patient, measure total variable cost of associated healthcare services and visits. Then compare the distribution of costs between randomized groups using the Wilcoxon rank-sum test, a non-parametric analogue of Student’s *t*-test.

Aim 3: Qualitatively understand patient perspective of CGM

Specific Aim 3a: Record patients’ self-reported willingness to participate in a CGM pilot

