7.0 STATISTICAL ANALYSIS

This study is a parallel randomized control trial that will evaluate the impact of CGM versus a standard fingerprick protocol, between and within randomized groups. The primary analysis (Specific Aim 1a) will measure the intervention effect on six-month change in HbA1c. The quantitative secondary analyses will measure the withinpatient longitudinal change in glycemic variability among CGM patients (Aims 1b-d) as well as the intervention effect on hypoglycemic events, healthcare utilization and cost (Aims 1e, 2a-b) between randomized groups. Additionally, for each of these aims, we will conduct exploratory sensitivity analyses: measuring provider variability and its effect, as well as looking at patient-level heterogeneity of treatment effect (HTE) to describe

subgroups of patients in whom the benefit of CGM might be amplified or attenuated. Technical details are provided in Section 7.1 *Statistical Considerations*.

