7.1 Statistical Considerations

The primary analysis (Aim 1a) will measure the intervention effect on the patient-level six-month absolute reduction in mean HbA1c. Since not all patients will have their final HbA1c test at six months exactly, we will estimate each patient's six-month reduction in HbA1c by interpolating/extrapolating from their assessments, given that their HbA1c levels were assessed on at least two occasions: baseline, and >3 months post baseline. Then, among patients with a sufficient number of occasions of HbA1c assessments, we will estimate their sixmonth HbA1c using generalized linear mixed models with patient-level random slopes and intercepts, with appropriate link function and distributional family [8]. The quantitative secondary analyses (Aims 1b-e, 2a-b) will use outcomes related to the longitudinal change in various metrics of glycemic variability (MAGE, C_v , range) as well as the frequency of hypoglycemic events, healthcare utilization, and cost. The secondary analyses will also use longitudinal data analysis to assess whether there is a significant reduction in glycemic variability over six months (Aims 1b-d) among those randomized to CGM, whether there is a significant reduction in hypoglycemic events over six months (Aim 1e) among those randomized to CGM, and to assess whether overall healthcare utilization and costs differ between randomized groups [9]. Accordingly, specific aims 1b-e will rely heavily on longitudinal data analysis within a multilevel/hierarchical framework [10], specifically using generalized linear mixed models. In the sensitivity analyses, provider variability will be accounted for using three-level (provider, patient, occasion), quasi-Bayesian generalized linear mixed models [11]. Finally, the sensitivity analyses exploring HTE will use generalized additive models (GAM) to identify subgroups of patients for whom CGM is likely to have a differential effect [12-13].

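### Aim 1e says the slope of hypoglycemia intensity makes CGM and finger-prick arms comparable, but the slope scales with each device's detection fraction, so a shared trend or drifting detection breaks the comparison

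*Combined protocol and SAP*

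**What the plan says.** The Aim 1e hypothesis in Section 2.0 is a between-arm one: "The patient-level six-month reduction in frequency of hypoglycemic events will be greater among those randomized to CGM than that among those randomized to control". The process paragraph measures each patient's change "as the patient-level slope of the six-month linear change in the so-called" intensity λ of an estimated nonhomogeneous Poisson process, and then "we will compare the distributions between randomized groups". It justifies this choice by saying that "it allows us to compare changes in frequency of hypoglycemic events between groups with different modes of monitoring (continuous vs daily".

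Section 7.0 also treats the aim as between-arm, listing "the intervention effect on hypoglycemic events, healthcare utilization and cost (Aims 1e, 2a-b) between randomized groups". Section 7.1 places Aims 1b-e within generalized linear mixed models but gives no link or offset for Aim 1e.

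The two arms observe glucose very differently. The CGM reads every five minutes (synopsis, study procedures). Controls follow whatever finger-prick regimen their physician has set, with no frequency stated (Section 3.0). Aim 1b itself says that infrequent readings cannot support MAGE, and Aims 1b-d are confined to the CGM arm.

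For Aim 1e the documents give no detection term, no reading-frequency adjustment, no common ascertainment, no named test and no definition of a hypoglycemic event. The nearest threshold is in Aim 1d: "time in range (which is defined by glucose levels from 70 to 180".

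**The concern.** A finger-prick regimen will miss many episodes that a sensor catches. Fitting an intensity to the detected events does not restore the missed ones: it estimates the intensity of detected events. Differencing over time removes neither the scale factor nor any change in it.

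Aim 1e is the only stated between-arm comparison of hypoglycemic events. A difference in either direction could therefore reflect the device and not the patients' hypoglycemia, while the protocol tells readers that the method deals with this.

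Both conditions for trouble are plausible here, though neither is documented:
- **Shared trend.** Both arms receive devices, apps and monthly contact (Sections 3.0 and 4.2), so both could change over time.
- **Drift in detection.** Sections 4.2 and 6.1 anticipate non-compliance and missing entries. Monthly resupply, check-ins and reminders limit drift but do not exclude it, and they do nothing about a shared trend.

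**Working it through.** The plan states no figure for Aim 1e, so there is none to reproduce.

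**Algebra.** Let λ(t) be the true rate and p(t) the fraction detected. Detected events have intensity p(t)·λ(t), with slope p·λ′ + p′·λ.

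- *Shared fall, constant detection.* True rate 2 to 1 per month in both arms; detection 0.9 (CGM) and 0.4 (finger-prick). Observed changes are 0.9 × (−1) = −0.90 and 0.4 × (−1) = −0.40, a spurious −0.50 favoring CGM. With finger-prick detection 0.1 the difference is −0.90 − (−0.10) = −0.80.
- *Finger-prick drift, flat 4 per month.* Detection 0.30 to 0.15 gives 4 × (−0.15) = −0.60 in controls and 0 in CGM: false harm.
- *CGM drift, flat 4 per month.* Detection 0.90 to 0.72 gives 4 × (−0.18) = −0.72 in CGM and 0 in controls: false benefit.
- *Same proportional drift, flat 4 per month.* CGM −0.72; finger-prick 0.30 to 0.24 gives 4 × (−0.06) = −0.24. The difference is −0.48.
- *Reversal.* If CGM truly falls by 0.4 and control by 1.0, with detection 0.9 and 0.25, the observed changes are −0.36 and −0.25. The arm that improved less looks better.

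**Simulation inputs.** From the documents: 100 analyzed (Section 7.2) and six months. Assumed: 50 per arm (no allocation ratio is stated), monthly counts, gamma between-patient variation (shape 2), identical true rates, CGM detection 0.9, finger-prick 0.4 to 0.1, rates and detection linear from month 1 to month 6. Per-patient least-squares slopes are compared by a two-sided 5% rank-sum test, 2,000 runs per scenario. The nominal rate is 2.5% in each direction.

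| Scenario (true events/month) | Result |
|---|---|
| Shared fall 0.5 to 0.4 | 4-11% false benefit |
| Shared fall 1 to 0.75 | 8-22% false benefit |
| Shared fall 4 to 3 | 22-58% false benefit |
| Shared fall 2 to 1 | 40-89% false benefit |
| Shared rise 3 to 4 | 20-57% false harm |
| Flat 4 (flat 1), finger-prick 0.30 to 0.15 | 39% (14%) false harm |
| Flat 4 (flat 1), CGM 0.90 to 0.72, finger-prick 0.3 | 44% (15%) false benefit |
| Flat 4 (flat 1), both down 20% | 22% (8%) false benefit |
| 4 to 3 with finger-prick 0.30 to 0.15 | 4% benefit, 2% harm (biases nearly cancel) |
| Flat, constant detection | 5-8% in total |

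Ranges run over finger-prick detection 0.4 to 0.1. Repeat runs agreed within about three percentage points. The size moves with the assumptions. With the change spread over months 0 to 6 and counts at month midpoints, the 2-to-1 range becomes 31-75%. With gamma shape 0.5 it is 23-69%, and with shape 10 it is 49-94%.

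**The choice of test matters.** With flat rates and constant detection the mean slopes are equal, and the rank-sum test stays near nominal. The slope distributions still differ in spread. A Kolmogorov-Smirnov test, which the plan's wording permits, rejects in about 7-9% of flat runs at finger-prick detection 0.4 and about 70-84% at 0.1.

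**Would a log scale cure it?** Since log(pλ) = log p + log λ, a constant p drops out of the slope. A log-link Poisson arm-by-time test (patient-clustered errors, 1,000 runs) gives 5-6% in total under constant detection, and 5-6% when both arms' detection falls 20%. Under one-sided drift at flat 4 (flat 1) it fails: CGM drift gives 25% (10%) false benefit, and finger-prick drift 92% (42%) false harm, worse than the slope. A correct exposure offset restores 6-7%. If readings halve but detection falls only to 0.22, or not at all, the offset itself produces 50% or 96% false benefit at flat 4.

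Power can fall too. With control flat and CGM truly halving by month 6, at 1 event/month and finger-prick detection 0.4 and 0.1, the slope test has 63% and 78% power and the log test 53% and 25%. At 4/month the figures are 99.5% and 100% against 97% and 66%.

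**The case against.** The best defense is that the plan leaves the estimator open. Aim 1e does not say how λ is estimated, and a log link within the Section 7.1 mixed models would cancel a constant detection fraction. That has some force, but Aim 1e specifies a linear change in λ itself, and Section 7.1 supplies neither a link nor an offset. Even a log link would not handle drift.

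Second, the size is unknown and could be small. Section 3.3.2 excludes patients hospitalized for hypoglycemia in the previous 18 months, and Section 3.3.1 admits type 2 patients with HbA1c from 6.5%, so event rates may be low. A mild-event threshold could still give high ones. This stands: the lower end of the range is close to nominal, and the upper end should not be read as typical.

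Third, a reader might infer that the slope should be replaced by a log-link rate ratio. The figures do not support that. The log scale is better for a shared trend, for equal proportional drift and for CGM drift, and worse for finger-prick drift and often for power. It also turns the hypothesis from absolute to relative reduction, which is the investigators' choice.

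Fourth, a reader might see a contradiction in Section 7.1, which asks "whether there is a significant reduction in hypoglycemic events over six months (Aim 1e) among those randomized to CGM". That sentence opens "The secondary analyses will also use longitudinal data analysis", so it may simply add a within-arm analysis. It needs a clarifying phrase and carries no weight here.

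**Conclusion.** The comparability statement in Aim 1e does not hold in general. The tempting stronger reading, that the slope comparison is invalid in every case, is not supported: with no trend and constant detection the mean slopes agree and a rank-sum test behaves. It also holds if detection is the same in both arms throughout.

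The algebra is certain. The size rests wholly on assumed inputs: false CGM benefit from a shared fall runs from 4-11% to 40-89% across the scenarios tried, a shared rise produces false harm, and opposing biases can cancel.

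This should be fixed, in proportion: it affects one secondary aim of a pilot and leaves the HbA1c primary analysis untouched.

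**What to change.** 1. In Section 2.0, Aim 1e, delete the comparability sentence. Alternatively, replace it with a statement that the slope comparison is valid only with constant detection and no shared trend, or with equal detection in both arms.
2. Keep the between-arm comparison but label it exploratory. Name a two-sided location test (the rank-sum test of Aim 1a would serve) and set one event rule for both devices before analysis, including how consecutive low CGM readings are merged.
3. Report control readings per week and CGM wear time, by arm and month.
4. Add, as a sensitivity analysis and not a replacement, an arm-by-time rate ratio from a log-link count model, with and without an exposure offset. State its limits: it removes constant unequal detection but not drift, is worse than the slope when only finger-prick detection drifts, and can have lower power.
5. In Section 7.1, say whether the within-CGM reduction is an additional descriptive analysis.

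The cost is some rewording, a tabulation and one extra model, plus a weaker between-arm conclusion on hypoglycemia. Control reading counts may be incomplete, because Section 4.2 allows manual entry when the Bluetooth transfer fails.

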3.2 Number of Subjects

We aim to recruit 125 patients, expecting 20% attrition by the six-month follow-up, yielding about 100 patients for analysis (see *7.2 Sample Size and Power*).

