5.2 Voluntary Withdrawal of Consent

Subjects shall have the ability to withdraw consent for study participation and/or the use of their clinical information at any time and for any reason, without penalty or loss of benefit to which the subject is otherwise entitled, by contacting the Principal Investigator or a designated member of his research team, preferably in writing and addressed to the Principal Investigator at the address indicated on the cover page of this protocol.

In the case a subject enrolled in this study decides to withdraw from the research, or an Investigator decides to terminate a subject's participation, study investigators must follow accepted standard practices regarding the management of collected data about these subjects, as follows:

- Investigators must document in the research record each instance of a subject withdrawal, including the reasons for the withdrawal, if known.
- If the subject withdraws and does not consent to continued follow-up and collection of clinical information, the investigator(s) will discontinue access to the subject's medical record or other confidential records, for purposes related to the study.
- Following the subject's withdrawal from the study, the Study Team will no longer contact the subject nor have access to his/her medical records for research purposes (unless specific informed consent has been obtained as described above).

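### Aims 2a and 2b compare raw six-month visit counts and cost totals with no observed-time denominator, censoring rule or analysis set for patients whose records close early

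*Combined protocol and SAP*

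**What the plan says.** Section 2.0 defines both outcomes patient by patient.

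- **Aim 2a.** The hypothesis is "The count of primary care, specialist, and emergency department visits or hospital stays over six months will be fewer among those randomized to CGM". The process is "For each patient, count their visits to a primary care provider or specialist or emergency department/hospital admission", and then to "compare the distributions of visit counts between randomized groups using a Poisson test, aggregated as well as stratified by visit type". Further metrics are offered as optional, among them "emergency department visit per 1000 rate, overall and for patients with diabetes, and hospitalization per 1000 rate related to diabetes".
- **Aim 2b.** The process is "For each patient, measure total variable cost of associated healthcare services and visits". A rank-sum test on these totals then compares the arms. Its hypothesis also refers to six months.
- **Data source.** Section 4.2 lists utilization and cost among the items drawn from medical records and visits.
- **Withdrawal.** Under Section 5.2, if a patient withdraws and does not agree to further collection, "the investigator(s) will discontinue access to the subject's medical record or other confidential records, for purposes related to the study". Access continues only with specific consent.
- **Attrition.** Section 3.2 plans for 125 patients, "expecting 20% attrition by the six-month follow-up", leaving about 100 to analyse.

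For utilization and cost, Section 7.1 says only that the arms will be compared. It gives no person-time, offset, censoring rule or analysis set. Its requirement of an HbA1c value more than three months after baseline belongs to the primary analysis.

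**The concern.** A count or a cost total means something only alongside the time over which it was collected. A patient whose record closes after one month has about one month of visits and cost, but the comparison as written gives that total the same standing as a six-month one. Early closure therefore looks like low use, which is what both hypotheses predict for CGM. If closure is more common or earlier in the CGM arm, part of any apparent saving is an artefact; if in the control arm, a real saving is masked.

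The plan handles the same difficulty elsewhere. Section 7.1 adjusts HbA1c for unequal timing, and Aim 1e uses an event intensity so that differently monitored arms can be compared. Aim 2 has no counterpart. Section 1.1 treats the effect on cost and utilization as critical to know before more clinic sites are added, so these secondary results will be used.

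**Working it through.** **Inputs from the documents.** 125 enrolled, 20% attrition, 100 analysed (Sections 3.2 and 7.2). The arithmetic reproduces: 125 × 0.8 = 100. The documents give no power figure, visit rate, cost distribution or attrition split for Aim 2.

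**Assumed inputs.** 1:1 allocation (about 62 per arm), two-sided 5% level, no true effect, mean 6 visits per six months, Poisson counts, exit times uniform over six months, lognormal cost with log-scale SD 1. Let p be the share leaving an arm and c the share of leavers whose records close.

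**Step 1: expected ratio.** The mean observed fraction in an arm is 1 − p·c/2.

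- Equal 20% leaving, all closed: 1 − 0.20/2 = 0.90 in both arms. Recorded visits fall from 6.0 to 5.4, and the ratio stays at 1.
- 30% CGM vs 10% control, all closed: 0.85/0.95 = 0.895.
- The reverse split: 0.95/0.85 = 1.118.
- 30% vs 10%, half closed: 0.925/0.975 = 0.949.
- 25% vs 15%, all closed: 0.875/0.925 = 0.946. Half closed: 0.9375/0.9625 = 0.974.

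**Step 2: hand check of the Poisson test at 30% vs 10%, all closed.** Expected totals are 62 × 6 × 0.85 = 316.2 and 62 × 6 × 0.95 = 353.4. The log ratio is ln(0.895) = −0.111, with SE √(1/316.2 + 1/353.4) = 0.077, so z ≈ 1.44. The chance of exceeding 1.96 is about P(Z > 0.52) = 30%. Random exit times add a little variance, so simulation should come out slightly higher.

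**Step 3: simulation** (3,000 trials per scenario in most runs; ranges are across separate runs with 62 vs 62 or 62 vs 63 patients).

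| Leaving, CGM vs control | Leavers' records closed | Raw-count Poisson rejects | Rank-sum on cost rejects |
|---|---|---|---|
| 20% vs 20% | all | about 9% | about 5% |
| 30% vs 10% | all | 31–33% | 13–14% |
| 30% vs 10% | half | 12–13% | about 7% |
| 30% vs 10% | a quarter | about 7% | about 6% |
| 25% vs 15% | all | 14–16% | not available |
| 25% vs 15% | half | 8–9% | about 6% |

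Under the same pure Poisson assumptions, a person-time base brings the count test back to about 5% (4.6–5.5% across the scenarios run).

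**Step 4: is person-time enough?** Let patients' underlying rates vary with gamma variance 0.5 (assumed). At mean 6 the per-patient variance is 6 + 0.5 × 36 = 24, four times the Poisson value. The test's standard error is then half what it should be, and the rejection rate is about P(|Z| > 1.96/2) = 33%. Simulation with person-time gave 30–33%. The time base removes the bias from unequal observation but leaves this problem untouched.

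**The case against.** A reader might infer that the plan definitely scores early leaving as low use and so favours CGM. The documents do not support that. They speak of about 100 patients for analysis, which allows a completers-only reading, and since both outcomes are defined over six months, a one-month leaver could be treated as missing. The plan also does not say when utilization is extracted; if that happens after access ends, a leaver's data could be absent altogether. The wording of Aim 2a points towards keeping leavers but does not settle it.

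Other points against the concern also have force.

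- **Attrition is not record closure.** Section 5.4 does not close the records of patients lost to follow-up, and Section 5.2 allows continued collection with consent. The all-closed figures are an upper end.
- **A 30% vs 10% split is large.** If both arms truly lose 20%, the leaver difference has SD √(2 × 62 × 0.2 × 0.8) = 4.45. A gap of 12 or more has probability of about P(|Z| > 11.5/4.45 = 2.58), or 1%. Such a split would have to come from a real difference in leaving. The adhesive risk in Section 4.3 and the exit-survey question on disappointment with assignment make one conceivable in either direction; neither predicts it.
- **The per-1000 rates** are optional and may be clinic-population metrics, since every trial patient has diabetes. A claim that they are understated by 10% is not supported.
- **A Poisson test can take a time base.** True, but none is specified.

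What survives is that the stated comparison uses raw totals and does not say how unequal observation is handled.

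**Conclusion.** The point holds as a gap in the specified method, for secondary aims only; the primary HbA1c analysis and the sample size are unaffected. Either way of filling the gap has a cost: keeping leavers mixes short and full observation, and dropping them gives up the randomized comparison.

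Equal closure lowers recorded use (by about 10% if all of 20% close) and leaves the ratio near 1. Bias between arms requires closure to differ by arm, and nothing in the documents shows which way it would go. With half of leavers' records closed, the count test is moderately inflated (8–13% in the unequal splits examined) and the cost test is close to nominal (6–7%); with all closed, the count test is badly inflated at the larger split. All these figures rest on assumed visit rates, exit times and attrition splits. It would also be too strong to say that person-time alone repairs Aim 2a, because between-patient variation can still leave about 31% false rejection.

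**What to change.** - **Aim 2a.** Include all randomized patients. Compare visits per observed patient-month, with days from randomization to day 180, or to the end of record access if earlier, as the offset. Use a robust or overdispersed variance, for example negative binomial, in place of the plain Poisson test.
- **Aim 2b.** Treat cost as censored at the end of record access, or more simply compare cost per observed month.
- **Data.** Record the date on which record access ends. Section 5.2 requires the withdrawal and its reasons to be documented but does not mention this date. Report observed days by arm beside both results.
- **Withdrawal.** Ask each leaver whether record-only collection may continue to day 180. Section 5.2 already allows this with consent, and it needs no further contact.
- **Per-1000 rates.** Use the same denominator only if they are calculated on trial patients.

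The cost is a few sentences in the plan, one added date field, one question at withdrawal and slightly wider intervals. An offset does not correct for withdrawal that is itself related to a patient's use of care, which is a further reason to keep record access open where the patient agrees.

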3.3.1 Inclusion Criteria

- Type 1 or type 2 diabetes mellitus with a HbA1c $\geq 6.5\%$
- Patients that are currently managing their glucose levels for diabetes with a glucose meter (or will be prescribed one by their healthcare provider)
- Patients that are treated within the four Reimagine Primary Care clinics (Cottonwood Family Medicine, Cottonwood Senior, Avenues Internal Medicine, and Holladay Internal Medicine).
- Patients 18-80 years of age

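### Aim 2a tests visit counts with a Poisson test that assumes variance equals mean; an assumed two-sided 5% error becomes about 7% to 38% if the variance is 1.25 to 5 times the mean (assumed), mainly for aggregate and frequent visits

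*Combined protocol and SAP*

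**What the plan says.** The Aim 2a process in Section 2.0 has the team count each patient's primary care, specialist and emergency or hospital visits. It continues: "Next, compare the distributions of visit counts between randomized groups using a Poisson test, aggregated as well as stratified by visit type". It names no dispersion term, robust variance or follow-up offset, and it states no alpha or sidedness.

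Section 7.1 adds that longitudinal methods will be used "to assess whether overall healthcare utilization and costs differ between randomized groups", but it names no count model and ties the mixed-model framework specifically to Aims 1b to 1e. Section 7.0 says that "for each of these aims, we will conduct exploratory sensitivity analyses". In these, according to Section 7.1, "provider variability will be accounted for using three-level (provider, patient, occasion), quasi-Bayesian generalized linear mixed models".

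Cost, the companion outcome in Aim 2b, is handled at patient level: "Then compare the distribution of costs between randomized groups using the Wilcoxon rank-sum test".

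**The concern.** A two-sample Poisson test takes its standard error from the total number of visits alone. That is right only if all patients in an arm share one visit rate. Section 3.3.1 admits type 1 and type 2 diabetes, "Patients 18-80 years of age" and four clinics, and Section 1.1 describes patients with four comorbidities on average. Individual rates will vary in such a group. Variation in rates on top of Poisson counting pushes the variance above the mean, and the test then understates the uncertainty.

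Section 1.1 treats knowledge of the effect on utilization as necessary before the clinic programme is extended. With the test as named, a few frequent users falling in one arm by chance could produce a nominally significant difference in aggregate visits, in either direction.

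Observed time may also differ between patients. Under Section 5.2, if a subject withdraws and "does not consent to continued follow-up and collection of clinical information, the investigator(s) will discontinue access" to the medical record, later visits are not seen. This second effect is not quantified here.

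**Working it through.** **Inputs from the documents.** 125 enrolled with 20% attrition (Sections 3.2 and 7.2): 125 × 0.8 = 100 analysed, which reproduces the plan's figure. The plan gives no visit rate, variance or power for Aim 2a, so there is no further figure to reproduce.

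**Assumed inputs.** 1:1 allocation (50 per arm), two-sided 5%, equal follow-up, no true difference, a mean of 4 visits in six months for the aggregate, and a variance/mean ratio φ from 1.25 to 5.

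**Standard error.** Each arm is expected to have 50 × 4 = 200 visits. The Poisson standard error of the log rate ratio is √(1/200 + 1/200) = 0.10. The true value is 0.10 × √φ: 0.14 at φ = 2 and 0.22 at φ = 5.

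**Type I error by formula.** Actual error = 2Φ(−1.96/√φ). At φ = 2, 1.96/1.414 = 1.386, giving 16.6%.

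**Type I error by simulation.** Gamma-Poisson counts, 50 per arm, mean 4, 10,000 runs per cell:

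| φ | Formula | Exact Poisson test | Quasi-Poisson | Wilcoxon |
|---|---|---|---|---|
| 1 | 5.0% | 4.2% | 4.7% | 4.8% |
| 1.25 | 8.0% | 7.3% | 5.1% | 4.8% |
| 1.5 | 11.0% | 9.9% | 5.1% | 4.8% |
| 2 | 16.6% | 15.6% | 5.0% | 4.8% |
| 3 | 25.8% | 24.6% | 5.4% | 5.1% |
| 5 | 38.1% | 36.5% | 4.9% | 4.9% |

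Robust-variance Poisson regression stayed between 4.8% and 5.6%. At mean 2 the exact test gave 6.9% at φ = 1.25 and 36.2% at φ = 5. A one-sided 5% test gives, by formula, 7.1% at φ = 1.25 and 23% at φ = 5.

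**Rare visits.** 4,000 runs per cell, exact Poisson test:

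| Mean visits | φ = 1.1 | φ = 1.25 | φ = 1.5 | φ = 2 |
|---|---|---|---|---|
| 0.1 | 2.7% | 3.6% | 5.2% | 9.9% |
| 0.3 | 3.6% | 5.3% | 7.9% | 12.8% |

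Over φ = 1 to 3, Wilcoxon held 4.4% to 5.0% at mean 0.1 and 4.9% to 5.5% at mean 0.3. Permutation of the mean difference held 1.4% to 2.1% and 2.9% to 3.7%. Quasi-Poisson is unsuitable at mean 0.1: its error was 0.4% to 1.9%, and it could not be estimated in 1% to 13% of runs because an arm had no events.

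**Why frequent visits suffer most.** If patient rates have squared coefficient of variation 0.5 (assumed), then φ = 1 + 0.5 × mean. At 0.1 visits φ = 1.05 and the formula gives 5.6%; at 4 visits φ = 3 and it gives 25.8%; at 8 visits φ = 5 and it gives 38.1%.

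**The case against.** The strongest reply is that the plan may not rest on the bare test. Section 7.0 refers the reader to 7.1 for technical detail, 7.1 mentions longitudinal analysis of utilization, and the three-level models include a patient level that could absorb between-patient spread. This shows that the plan is ambiguous, but it does not repair the test. Section 7.1 assigns mixed models to Aims 1b to 1e, the three-level models are exploratory and aimed at provider variability, and nothing says that either replaces the test named under Aim 2a.

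The size rests on assumptions, and that stands. Alpha, sidedness, allocation, visit mean and dispersion are all assumed, and no document supports a ratio as high as 5. At mean 4 the exact test is at about 5.0% and 5.6% for ratios of 1.05 and 1.1, so the error is negligible if dispersion is slight. The range of about 7% to 38% also spans two versions of the test, 7.3% to 36.5% exact and 8.0% to 38.1% by formula, because the plan does not say which Poisson test it means.

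Two smaller points also stand. A Poisson rate test can take exposure time, so silence about an offset does not prove that follow-up will be ignored. And for rare visits with modest dispersion the exact test is already near or below 5%, so the gain there is small. Finally, Aim 2a is a secondary aim of a pilot with no decision rule attached, which limits the consequences.

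**Conclusion.** The concern holds. As written, Aim 2a uses a test whose variance assumption is implausible for this sample, and no other part of the plan replaces it. The direction of the error for aggregate and frequent visits is clear. Its size is conditional: under the assumptions listed above, roughly 7% to 38% in place of 5% over variance/mean ratios of 1.25 to 5. A ratio of 2 already triples the nominal level. For emergency visits and admissions the exact test stays near or below 5% unless dispersion is marked. This should be fixed, but the consequence is confined to a secondary aim; the primary HbA1c comparison uses a Wilcoxon test and is untouched.

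**What to change.** In the Aim 2a process, replace the Poisson test with a Poisson regression of each patient's visit count on arm, with estimated dispersion (quasi-Poisson) and log observed follow-up days as offset. Report the rate ratio with its 95% confidence interval for all visits and for primary care and specialist visits. Robust variance is an alternative; so is a negative binomial model, though it was not simulated here.

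For emergency visits and admissions, use a Wilcoxon rank-sum or permutation test on per-patient counts, taken per observed day if follow-up differs. Wilcoxon stayed closer to 5% in the simulations and is already the Aim 2b method.

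State alpha and sidedness. In Section 7.1, say that this is the Aim 2a analysis and that the three-level models are sensitivity analyses, so that Sections 2.0 and 7.1 agree.

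The change costs a few sentences and standard code, with no new data. The price is wider intervals and less apparent power. With 50 per arm and a control mean of 4 (assumed), the rate ratio (RR) detectable with 80% power solves |ln RR| = 2.80 × √(φ(1/200 + 1/(200 RR))). It moves from 0.74 at φ = 1 to 0.71, 0.64 and 0.45 at φ = 1.25, 2 and 5.
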